7.4 Surgery

7.4.1 Patient Assessment

After the patient has been identified as a candidate for the trial, the surgeon will assess the patient and will determine:

1. Exact height and location of tumor with regards to the anal margin as measured by a rigid or flexible proctoscope and/or digital exam.
2. Mobility of tumor as assessed if possible by rectal exam
3. Type of surgical procedure: Abdomino-perineal resection vs. sphincter saving procedures, which will include colo-anal with mucosectomy vs. stapled anastomosis.

7.4.2 Patient Preparation

Routine pre-operative assessment will be undertaken as standard care. Efforts will be made for the patient to be seen by a stomatherapist pre-operatively in order to mark the future site of either temporary ileostomy or permanent colostomy. Bowel preparation, perioperative antibiotics, and venothromboembolic prophylaxis will be encouraged and administered at the discretion of the treating facilities. Skin preparation, glucose monitoring, and temperature regulation will be at the discretion of the treating surgeon and facility.

7.4.3 Tumor Assessment

The following items will be assessed at the time of surgery either before the procedure begins or once the specimen has been removed.

1. Macroscopic response to brachytherapy (complete vs. partial vs. non response)
2. Height between tumor bed and anal margin, to assess feasibility of either colo-anal anastomosis vs. stapled anastomosis vs. abdomino-perineal resection (APR).
3. Location of the tumor on the bowel wall (anterior/posterior).

The pathologist should be orientated to the position of the tumor and should open the lumen of the specimen so that the response can be directly observed. We follow the criteria outlined by Mandard et al. with tumor regression grade (TRG) 1-2 demonstrating a good response to therapy (52).

7.4.4 Surgical Technique

Surgery should occur between 8 and 12 weeks from the completion of neoadjuvant therapy.

Patients will be positioned in lithotomy. The use of ureteral stents will be at the discretion of the treating surgeon. Open and minimally invasive techniques are allowed. If preservation of the anal sphincter muscles is planned, a standard laparotomy will be undertaken. An assessment of the liver, peritoneum, pelvic organs (uterus/ovaries) should be performed. The objective of the operation is a curative

procedure with full total mesentery excision (TME) of the rectum. It will be expected that all attempts to perform a high ligation of the IMA will occur and that the nodes within this portion of the mesentery will be carefully examined. The plane between the fascia propria of the rectum and the presacral fascia will be entered in the midline posteriorly. Every attempt will be made to identify the hypogastric nerves along the pelvic side wall and the findings will be recorded as injured or preserved (See Appendix VI). It is expected that all tumors located in the mid and lower rectum will be removed with a complete TME. All attempts will be made to achieve at least a 3-cm margin on the mesorectum and a 1-cm mucosal margin. If the margin is in question, additional margin should be taken. A frozen section may be performed at the discretion of the treating surgeon. The surgeon will record their assessment of the TME as either complete, nearly complete, or incomplete recording difficulty encountered. It will be at the discretion of the surgeon to perform either a straight end-to-end or side-to-end anastomosis with or without a colonic pouch or coloplasty. Evaluation of the anastomosis will be performed from the abdominal side, i.e., tension-free anastomosis and from the perineal side, i.e., complete ring of the anastomosis and negative air test. All patients undergoing a resection with re-anastomosis will have a diverting loop ileostomy performed. If an APR is performed, the perineum will be removed in an oncological fashion with preservation of the radial margin either at the start of the procedure or at the end of the procedure. The perineum will be closed in a method which is at the discretion of the treating surgeon and the patient will be given a permanent stoma.

Abdominal or perineal drainage will be left to the discretion of the surgeon.

7.4.5 Post-Operative Assessment

[figure not shown]
Standard post-operative care will be undertaken. Length of stay, transfusion requirements, surgical site infections (including clinical and sub-clinical anastomotic leaks), and venothrombotic events as captured by the National Safety Quality Improvement Project (NSQIP) will be recorded. Any hospital mortality with cause of death will be recorded. Any other intraoperative findings such as perineal wound infection (for patients undergoing APR), anastomotic leak (managed with IR drainage vs. requiring return to OR), or intraabdominal abscesses will be recorded.

7.4.6 Follow-Up Evaluation

Patient will be considered for stoma closure 2 to 3 months after surgery or following additional chemotherapy. Prior to stoma closure, patient will have anastomosis evaluation by either standard contrast radiography direct in the rectum and or by rectal exam with sigmoidoscopy. Any abnormal finding will be recorded and may delay stoma closure.

7.4.7 Postoperative Adjuvant Chemotherapy

Per standard of care and at the discretion of the treating physician, approximately 6-10 weeks after surgery, patients will receive modified FOLFOX6 adjuvantly after resection for 6 months (12 cycles). Below is a recommended regimen but final plan is at the discretion of treating physician.

FOLFOX6:**Day 1:**

Oxaliplatin: 85 mg/m² in 500ml glucose 5% solution, 2-h infusion

Folinic acid (FA) 400mg/m² in 250ml glucose 5% solution, 2-h infusion simultaneously with the oxaliplatin infusion

5-Fluorouracil (5-FU) bolus 400mg/m² following the oxaliplatin/FA infusions

5-FU continuous infusion 2400 mg/m², 46-h infusion following the 5-FU bolus

Cycle length: 14 days (2 weeks)

Duration of treatment: 12 cycles

7.5 Follow-Up Assessments

Patients will be followed per standard of care. For study purposes, an initial follow-up will occur post-operatively and then annually by PI and/or study team members. Every effort made to collect any SAE's or hospitalizations that occurred in the year prior. QOL will be collected per the study calendar. In the event this cannot be completed in person or online, it will be mailed out.

7.5 Supportive Care

The following supportive care is recommended. However, it is ultimately at the discretion of the treating physician.

7.5.1 Patients receiving Endo-HDR

Proctitis and rectal pain are the main side effects reported among patients receiving Endo-HDR. These symptoms are currently managed as follows:

- Cortifoam enema (all patients)
- Naproxen 375 – 500 mg (all patients; twice daily; discontinue 3 weeks before surgery)
- Acetaminophen with codeine 300/30 mg (patients experiencing mild to moderate pain; take 3 – 4 times daily as needed)
- Hydromorphone 2 mg (patients with severe pain only; take 3 – 4 times per day as needed)

7.5.2 Patients receiving External Beam Radiotherapy

Diarrhea, skin irritation, fatigue, urinary tract irritation, and decreased blood counts are the main side effects experienced during concurrent chemotherapy and pelvic radiation therapy. Standard supportive care measures may be used at the treating physician's discretion throughout the course of therapy, including antidiarrheal agents (loperamide, etc.), skin creams, and phenazopyridine (Pyridium). Specific guidelines for dose-reducing capecitabine as needed are given in Section 7.3.5.

7.6 Subject Withdrawal/Removal

Patients will be removed from the study for the following reasons:

- Unacceptable toxicity from therapy. Toxicity must be appropriately documented.
- Development of intercurrent, non-cancer related illness that prevents either continuation of therapy or regular follow-up
- The patient decides to discontinue enrollment in the protocol at any time and for any reason
- Continuation of participation could be harmful
- Pregnancy
- The patient needs treatment not allowed in the study

All reasons for discontinuation of treatment must be documented.

- Patients who prematurely discontinue radiation treatment but undergo surgical exploration will be followed per the prescribed protocol schedule.
- Patients who prematurely discontinue radiation treatment and do not undergo surgical exploration will be followed for survival for five years.
- Patients who complete radiation treatment and do not undergo surgical exploration will be followed for survival for five years.

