4.2 Secondary Objectives

- Test whether clinical response based on functional imaging (PET, MRI) pre/post radiation (Endo-HDR vs. CRT) predicts for pathologic complete response.
- Utilize preoperative imaging response rates and clinical exam to determine whether Endo-HDR results in improved sphincter preservation rates when compared to CRT.
- Determine whether tumor (VEGF/EGFR status) and blood predict for pathologic response following neoadjuvant Endo-HDR vs. CRT.
- Compare acute and long-term toxicity as well as quality of life for both Endo-HDR and CRT.
- Compare locoregional control, distant metastasis and overall survival for both Endo-HDR and CRT.

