9. STUDY CALENDAR

Evaluation	Baseline ¹	RADIATION TREATMENT ⁷	Pre-Op ⁸	SURGERY ⁹	Post-Op ¹⁰	CHEMOTHERAPY ¹²	Post Surgical Follow-Up ¹³				
							1Y	2 Y	3Y	4Y	5Y
Informed Consent	X										
H&P	X		X		X		X	X	X	X	X
Performance Status	X		X		X		X	X	X	X	X
Pregnancy Test ²	X										
Concomitant Medications ³	X						X	X	X	X	X
Endoscopic Ultrasound ⁴	X										
Marker Placement ⁵	X										
Research Biopsy ⁵ (optional)	X										
FDG-PET/CT	X		X								
Pelvic MRI	X		X								
CT C/A/P							X	X	X	X	X
CBC w/ Diff, CMP	X		X		X		X	X	X	X	X
CEA	X		X		X		X	X	X	X	X
Testosterone ⁶	X		X					X	X	X	X
Biomarkers (optional, lead site only)	X		X		X			X	X	X	X
TME Evaluation							X ¹¹				
Toxicity Evaluation	X		X		X			X	X	X	X
QOL Surveys ¹⁴	X		X		X			X	X	X	X

1 Must be conducted within 6 weeks of RT initiation

2 Required for premenopausal women who have not been surgically sterilized within 1 month of RT initiation. All women of child-bearing potential must have negative pregnancy test (urine or serum).

3 Specifically: phosphodiesterase inhibitors, bi- and tri-mix injections, testosterone therapy, vaginal estrogen cream, and hormone replacement therapy

4 Must be conducted within 3 months of RT initiation

5 Must be conducted within 3 weeks of RT initiation; biopsy should include tumor and normal tissue sample (see Section 10.4.4)

6 Total and free testosterone level for male participants only

7 Patients will be monitored for toxicity weekly during RT

8 Within 4-8 weeks pre-surgery

9 Patients will undergo surgery 8-12 weeks from RT completion

10 Within 4-12 weeks post-surgery

11 Documentation must be complete within 1 week post-surgery

12 Adjuvant chemotherapy is standard and will not be monitored/tracked by the Principal Investigator or the study team

13 Annual follow-up appointments will be based on the date of surgery and have a tolerance window of +/- 30 days

14 See 9.1 for quality of life survey calendar

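### Randomised patients who have no surgery get survival follow-up only, so later recurrence and metastasis are not scheduled to be recorded and locoregional control is likely to be overstated

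*Combined protocol and SAP*

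**What the plan says.** Section 7.6 opens with a list of grounds for removal ("Patients will be removed from the study for the following reasons"), which includes unacceptable toxicity. It then sets follow-up according to radiation and surgery:

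- Radiation stopped early, surgery done: "Patients who prematurely discontinue radiation treatment but undergo surgical exploration will be followed per the prescribed protocol schedule".
- Radiation stopped early, no surgery: "Patients who prematurely discontinue radiation treatment and do not undergo surgical exploration will be followed for survival for five years".
- Radiation completed, no surgery: "Patients who complete radiation treatment and do not undergo surgical exploration will be followed for survival for five years".

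The schedule itself starts from the operation. Section 7.5 (Follow-Up Assessments) says that "an initial follow-up will occur post-operatively and then annually by PI and/or study team members". In Section 9 the yearly CT, CEA, examination, toxicity and quality-of-life entries stand under post-surgical follow-up, and footnote 13 reads "Annual follow-up appointments will be based on the date of surgery and have a tolerance window of +/- 30 days".

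Section 4.2 makes the affected outcomes a comparison between arms: "Compare locoregional control, distant metastasis and overall survival for both Endo-HDR and CRT". Section 14.5 censors patients last known to be alive at their last contact. It does not say which patients enter the locoregional and metastasis analyses, or how a primary tumour that was never resected counts. Section 14.4 states intention-to-treat for pCR only.

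**The concern.** Whether a patient reaches surgery is decided after randomisation and partly by outcome. Patients who progress, become inoperable or have severe toxicity are plausibly over-represented among those not explored. They are the patients whose later disease status the plan does not schedule to be collected.

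The censoring rule adds to this. A survival contact extends time at risk for local recurrence although nobody has to ask about recurrence. A living patient with pelvic failure could then contribute failure-free time up to that contact.

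The loss may also be unequal between arms. Section 3.1 cites acute grade 3-4 toxicity of <1% after Endo-HDR and 27% after preoperative chemoradiation, and the treatments differ in length. No non-surgery rate by arm is given. Dropping these patients instead would compare groups selected after randomisation.

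**Working it through.** **1. The plan's own figure.** The primary design figure is 80% power for pCR of 13% versus 30%, with 46 control and 92 Endo-HDR patients and a one-sided Fisher's exact test at 0.10 (Section 14.2.1). Exact enumeration over the two binomial distributions gives 0.802, so the figure reproduces. It does not depend on later follow-up. The plan gives no power or precision for locoregional control or metastasis.

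**2. Inputs for the follow-up gap.**

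- Randomised: 138 (Section 14.2.1).
- Drop-out after randomisation: <5% (Section 14.2.1). That this means no surgery is an assumption.
- Local recurrence after surgery: 5% at five years, from the cited Endo-HDR phase II series (Section 3.1), applied here to both arms.
- Local failure without surgery, r: not in the documents; varied from 0% to 100%.

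**3. Patients affected.** 0.05 × 138 = 6.9, and the plan says less than 5%, so at most 6. At 2:1 allocation that is about 4 Endo-HDR and 2 control.

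**4. Events.** Among the other 132 patients, 132 × 0.05 = 6.6 local recurrences are expected. Missed events are 6 × r. These are simple proportions without competing risks.

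- If the 6 patients are kept as event-free, the recurrence rate seen is 6.6/138 = 4.8%, and control is overstated by 6r/138.
- If they are excluded, or censored at the start, the rate seen is 5.0%, and control is overstated by (6.6 + 6r)/138 − 0.05.

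| r (assumed) | Missed events | True rate, (6.6 + 6r)/138 | Overstated, kept as event-free | Overstated, excluded |
|---|---|---|---|---|
| 0% | 0 | 4.8% | 0.0 points | −0.2 points |
| 5% | 0.3 | 5.0% | 0.2 points | 0.0 points |
| 30% | 1.8 | 6.1% | 1.3 points | 1.1 points |
| 50% | 3.0 | 7.0% | 2.2 points | 2.0 points |
| 100% | 6.0 | 9.1% | 4.3 points | 4.1 points |

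**5. Share of events.** For r from 30% to 100%, the missed share of all local failures runs from 1.8/8.4 = 21% to 6/12.6 = 48%.

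**6. Sensitivity.** With patients kept as event-free, the error is the non-surgical share times r and does not depend on the 5% rate. For r from 30% to 100%, a non-surgical share of 2% gives 0.6 to 2.0 points and a share of 10% gives 3.0 to 10.0 points.

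**The case against.** Several points on the other side stand.

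- **Bias as a fact.** A reader might infer that locoregional control will certainly be overstated. The documents do not establish that. They do not say how unresected disease counts, and they state no population for these endpoints. If unresected patients were counted as failures, control would not be overstated. Section 14.5 also measures local recurrence to death and names no recurrence event; that is a separate defect.
- **No data at all.** A reader might infer that these patients have no imaging or toxicity data. Section 10.1 schedules repeat MRI and PET/CT 4-8 weeks after radiation, whether or not surgery follows. Toxicity is checked weekly during radiation (Section 9, footnote 7), and Appendix II requires all SAEs to be collected. Section 7.5 refers to standard-of-care follow-up. The gap is in later recurrence, metastasis, late toxicity and quality of life.
- **Deaths are captured.** Survival contacts still give the deaths that enter the progression-free and metastasis-free endpoints as written. What is lost is mainly the date and site of failure.
- **A doubling of recurrence.** A reader might set 5% against about 10%. That needs local failure in every patient without surgery, all of it missed, and a full 5% of patients without surgery.
- **Meaning of drop-out.** It may include withdrawal of consent, for which no further data could be collected anyway.

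None of this supplies a scheduled disease assessment after restaging. The contrast between adjacent bullets in Section 7.6 makes this a stated rule and not an omitted detail.

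**Conclusion.** The concern holds for data collection after restaging. A rule that depends on surgery leaves recurrence and metastasis without scheduled collection in a group plausibly selected by outcome, while both are secondary comparisons between randomised arms. With censoring at last contact, overstated locoregional control is the likely result unless unresected disease is counted as failure.

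On the stated assumptions (drop-out means no surgery, 5% local recurrence after surgery, 30% to 100% local failure without it), at most 6 patients are involved and 1.8 to 6 events are missed, about 1.3 to 4.3 points of control. That is small in absolute terms but sizeable against about 6.6 observed events.

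A reader might go on to infer that the missing data favour one arm. The documents do not support this: the toxicity rates make unequal loss plausible, but without non-surgery rates by arm the net direction is unknown. The pCR analysis is not affected. The change should be made because data not collected cannot be reliably recovered at analysis.

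**What to change.** **Section 7.6 and Section 9, footnote 13.** For every randomised patient, with or without surgery, record recurrence and metastasis status with dates at the annual contacts, taken from standard-of-care records, and late toxicity and quality of life where obtainable. Date these contacts from randomisation and stop only on withdrawal of consent.

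**Section 14.5.** Analyse these endpoints in all randomised patients, censor disease endpoints at the last disease assessment, and add a sensitivity analysis that counts unresected or progressive local disease as locoregional failure. That count belongs in a sensitivity analysis because it would also class as failures any responders who decline surgery.

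**Cost.** Wording in three places and a small amount of extra annual data collection for a handful of patients. No additional mandated scans are needed, which matters because Section 7.7 charges procedures to patients or their insurers.

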7.7 Costs

Patients and/or their insurance companies will be responsible for the cost of all procedures and treatments under this protocol.

8. COORDINATING CENTER

8.1 Responsibilities

Johns Hopkins Hospital will serve as the coordinating center for this study. Coordinating Center functions will include:

1. Coordination of all data collection and analyses
2. On site monitoring/auditing of patient study charts and source documents at regular intervals that will be dictated by the rate of enrollment and treatment
3. Coordinating among the sites and reporting to a data monitoring committee. Each site will be expected to provide information on adverse events to their IRB as per each institution's procedures.

A complete discussion of the roles and responsibilities of the Coordinating Center and Participating Sites can be found in Appendix II.

9. STUDY CALENDAR

Evaluation	Baseline ¹	RADIATION TREATMENT ⁷	Pre-Op ⁸	SURGERY ⁹	Post-Op ¹⁰	CHEMOTHERAPY ¹²	Post Surgical Follow-Up ¹³				
							1Y	2 Y	3Y	4Y	5Y
Informed Consent	X										
H&P	X		X		X		X	X	X	X	X
Performance Status	X		X		X		X	X	X	X	X
Pregnancy Test ²	X										
Concomitant Medications ³	X						X	X	X	X	X
Endoscopic Ultrasound ⁴	X										
Marker Placement ⁵	X										
Research Biopsy ⁵ (optional)	X										
FDG-PET/CT	X		X								
Pelvic MRI	X		X								
CT C/A/P							X	X	X	X	X
CBC w/ Diff, CMP	X		X		X		X	X	X	X	X
CEA	X		X		X		X	X	X	X	X
Testosterone ⁶	X		X					X	X	X	X
Biomarkers (optional, lead site only)	X		X		X			X	X	X	X
TME Evaluation							X ¹¹				
Toxicity Evaluation	X		X		X			X	X	X	X
QOL Surveys ¹⁴	X		X		X			X	X	X	X

1 Must be conducted within 6 weeks of RT initiation

2 Required for premenopausal women who have not been surgically sterilized within 1 month of RT initiation. All women of child-bearing potential must have negative pregnancy test (urine or serum).

3 Specifically: phosphodiesterase inhibitors, bi- and tri-mix injections, testosterone therapy, vaginal estrogen cream, and hormone replacement therapy

4 Must be conducted within 3 months of RT initiation

5 Must be conducted within 3 weeks of RT initiation; biopsy should include tumor and normal tissue sample (see Section 10.4.4)

6 Total and free testosterone level for male participants only

7 Patients will be monitored for toxicity weekly during RT

8 Within 4-8 weeks pre-surgery

9 Patients will undergo surgery 8-12 weeks from RT completion

10 Within 4-12 weeks post-surgery

11 Documentation must be complete within 1 week post-surgery

12 Adjuvant chemotherapy is standard and will not be monitored/tracked by the Principal Investigator or the study team

13 Annual follow-up appointments will be based on the date of surgery and have a tolerance window of +/- 30 days

14 See 9.1 for quality of life survey calendar

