7.2 Endorectal Brachytherapy Radiation Therapy

7.2.1 Endorectal Brachytherapy Radiation Therapy

At the initial assessment, the surgeon will be asked to determine the likelihood of sphincter preservation. Endo-HDR is an outpatient procedure.

Patients will be treated with a daily dose of 6.5 Gy over four consecutive days for a total of 26 Gy. To administer Endo-HDR, patients will be placed in the lateral decubitus position to insert the endorectal applicator and then maneuvered into the supine position. Once in place, the applicator is secured to the plate/holder and an anal BB is placed at the anal verge. Dummy wires are inserted into the applicator and the patient is scanned using CT (2 mm slices). The radio-opaque (MRI safe-optimal) markers will guide application of the endorectal probe and assist with tumor delineation during IMRT treatment. For Endo-HDR, RT dose will be prescribed to the tumor radial margins or mesorectal node, whichever is greater not to exceed 3.5 cm from the mucosal surface. Prescribed dose will include a 1 cm CTV/PTV proximal and distal expansion excluding anal sphincter distally. However, when the GTV is close to the sphincter, the CTV should not be expanded distally into the

sphincter (treat GTV only). The endorectal applicator is flexible, with nine-channels using a high dose-rate remote after-loading system. Standard radiation procedures will be followed during Endo-HDR as outlined in the protocol. QOL will be assessed throughout the treatment process (see calendar). Endoscopic endorectal ultrasound (EUS) is obtained for tumor staging and magnetic resonance imaging (MRI) of the pelvis is used for tumor measurements (length and bulk evaluation).

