7.2.8 Dose Modifications

Every effort will be made to administer the entire radiation treatment to participants. Every effort will be made to limit the dose to the bladder, femoral heads, small bowel, vagina, uterus, and/or penile bulb.

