7.3.4 Treatment Break Outline

Pursuant with RTOG 0822: "Treatment interruptions are discouraged; however, they may be necessitated by uncontrolled diarrhea or other acute complications. The reason for and length of any such interruption must be documented. If the sum total of such interruptions exceeds 5 normally scheduled treatment days, this would constitute a major treatment violation. A minimum of 4 daily radiation therapy treatments are required in any given week. Any missed radiation treatments will be made up at the end of the treatment schedule, such that the total number of delivered 1.8 Gy fractions remains 28. If chemotherapy is held, radiation therapy will continue."

Toxicity	XRT Dose
Grade 2 thrombocytopenia	Continue at current dose.
Grade 3 thrombocytopenia	Hold until recovery to grade ≤ 1 , then resume.
Grade 4 thrombocytopenia	Hold until recovery to grade ≤ 1 (platelets $\geq 75 \times 10^9/L$), then resume.
Grade 3 neutropenia	Hold until recovery to grade ≤ 1 , then resume.
Grade 4 neutropenia	Hold until recovery to grade ≤ 1 , then resume.
Grade ≥ 3 febrile neutropenia	Hold until resolution of fever and neutropenia to grade ≤ 1 . Hold until the ANC $\geq 1,500/\text{mm}^3$ and fever has resolved. Then resume treatment.

References:

RTOG 0822 Protocol, Section 6 (Radiation Therapy)

<http://www.rtog.org/ClinicalTrials/ProtocolTable/StudyDetails.aspx?action=openFile&FileID=4663>

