7.3.5 Capecitabine (Xeloda)

Capecitabine shall be delivered at $825\text{mg}/\text{m}^2$ BID during IMRT radiotherapy. Dose modification shall occur as follows:

- If $\text{ANC} < 1000/\text{mm}^3$ capecitabine will be held until the blood counts recover above these values and the patient can resume full dosing
- If platelet count $< 100,000/\text{mm}^3$, capecitabine will be held until the blood counts recover above these values and the patient can resume full dosing

Event Name	Hand-Foot Skin Reaction
Grade of Event	Management/Next Dose for Capecitabine
\leq Grade 1	No change in dose
Grade 2	Hold until \leq Grade 1. For the first appearance resume at 100% of the dose. For the second appearance, dose reduce to $650\text{ mg}/\text{m}^2$ For the third appearance, dose reduce to $500\text{ mg}/\text{m}^2$ For the fourth appearance, discontinue.
Grade 3	Hold until \leq Grade 1. For the first appearance, dose reduce to $650\text{ mg}/\text{m}^2$ For the second appearance, dose reduce to $500\text{ mg}/\text{m}^2$ For the third appearance, discontinue.
Grade 4	Hold until \leq Grade 1. For the first appearance, dose reduce to $500\text{ mg}/\text{m}^2$ For the second appearance, discontinue.

Event Name	Diarrhea
Grade of Event	Management/Next Dose for Capecitabine
\leq Grade 1	No change in dose
Grade 2	For the first appearance, dose reduce to $650\text{ mg}/\text{m}^2$ For the second appearance, dose reduce to $500\text{ mg}/\text{m}^2$ For the third appearance, discontinue. ¹
Grade 3	For the first appearance, dose reduce to $650\text{ mg}/\text{m}^2$ For the second appearance, dose reduce to $500\text{ mg}/\text{m}^2$ For the third appearance, discontinue. ¹

¹Capecitabine may be discontinued at the discretion of the investigator

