14.5 Analysis of Secondary Endpoints

Secondary endpoints of this phase II trial include toxicity, quality of life, locoregional control/distant metastasis, overall survival, and correlative analyses of biomarkers and functional imaging changes.

The acute and chronic toxicity and adverse events will be summarized in frequency tables by type and grade for each arm and will be compared between arms using Fisher's exact tests.

Quality of life will be assessed via EORTC QLQ-C30 (v3.0) questionnaires as mentioned above. Scoring will be based on procedures outlined by the EORTC. For our study population of rectal cancer patients, the analysis will be focused on general and colorectal model regarding urinary/bowel toxicity, sphincter function, and sexual dysfunction. For each module, summary statistics of the scores will be reported at baseline and each follow-up time. After confirming that there are no baseline differences in quality of life across the two treatment arms using independent samples t-test, changes in quality of life scores from pre- to post-treatment will be computed, and the difference between these change scores will be evaluated by paired-sample t-tests. We will compare the quality of life scores at each endpoint as well as the differences between the two arms using two-sample t-test. Given the plurality of comparisons, p-values <0.01 will be considered statistically significant. In addition, mixed effect models will be used for assessing the quality of life change over time and comparing the two treatment arms. For instance, mixed effects models will be used to assess changes in QOL over time first in all study patients and then to compare the effects of the two treatment arms on change in QOL over time. Need for sexual aids will be compared in a descriptive fashion between the two cohorts.

Overall survival, distant metastases free survival, progression free survival, and local recurrence will be measured from the date of randomization to the date of death due to any causes. Patients last known to be alive are censored at date of last contact. Kaplan-Meier curves will be used to characterize overall survival in each arm and log rank test will be used for the comparison.

The analysis of correlative endpoints of imaging and biomarkers will be exploratory.

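### Section 14.5 compares acute toxicity by type and grade, but the plan checks the arms for different lengths of time and applies a different recording threshold to each, so the tables are hard to read in either direction

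*Combined protocol and SAP*

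**What the plan says.** Section 14.5 states that acute and chronic toxicity will be "summarized in frequency tables by type and grade for each arm and will be compared between arms using" Fisher's exact tests. It gives no time window for acute toxicity and no significance level for these tests.

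The rules that feed those tables are elsewhere:

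- **Checks during radiation.** Study Calendar, footnote 7: "Patients will be monitored for toxicity weekly during RT". The next scheduled toxicity evaluation in both arms is Pre-Op.
- **Length of radiation.** Endo-HDR, section 7.2.1: "Patients will be treated with a daily dose of 6.5 Gy over four consecutive days for a total of 26 Gy". Control, section 7.3.4: missed treatments are made up "such that the total number of delivered 1.8 Gy fractions remains 28".
- **Pre-Op timing.** Footnote 8: "Within 4-8 weeks pre-surgery". Footnote 9: "Patients will undergo surgery 8-12 weeks from RT completion".
- **Count-based holds.** Control has neutrophil and platelet rules for radiation (7.3.4) and for capecitabine (7.3.5: "capecitabine will be held until the blood counts recover above these values and the patient can resume full dosing"). Section 7.2.8 gives Endo-HDR no such rule, only that "Every effort will be made to administer the entire radiation treatment to participants". The calendar lists no CBC during radiation for either arm.
- **Recording threshold.** Section 11.8 limits recording of chemotherapy-attributed side effects to grade 3 or higher. Section 11.6 records all radiation-related events, and section 11.5 sets no grade limit for Endo-HDR.
- **Between visits.** Section 11.12.1 records events that require medical attention.

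**The concern.** Lower acute toxicity is part of the hypothesis (section 1), and comparing toxicity is a secondary objective (4.2). Section 3.1 presents absence of hematologic toxicity as an advantage of Endo-HDR. A by-grade comparison can support such claims only if an event of a given grade has a similar chance of reaching the case report form in each arm.

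Two rules break that condition even when sites follow the protocol exactly. Tying weekly checks to radiation means Endo-HDR patients are in the trial during weeks 2 to 6 but have no scheduled check then. The grade 3 threshold in 11.8 means a mild event attributed to capecitabine is dropped in control, while the same event in Endo-HDR is kept. The first rule favors Endo-HDR. The second, at grades 1 and 2, favors control. A difference in a row of the table, or the lack of one, could then come from the recording rules rather than from the regimens.

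**Working it through.** **1. Number of scheduled checks.** Endo-HDR: 4 daily fractions, 4/5 = 0.8 week, so 1 weekly check. Control: 28/5 = 5.6 weeks, so about 6. This agrees with the plan's own statement in section 1 of 1 week against 6. Adding the shared Pre-Op visit gives 2 against about 7.

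**2. What can be missed in Endo-HDR.** Between the end of Endo-HDR and Pre-Op, an event is recorded under 11.12.1 if it requires medical attention. By the footnotes, Pre-Op falls between 8 − 8 = 0 and 12 − 4 = 8 weeks after radiation; section 10.1 puts the repeat imaging at 4 to 8 weeks. The exposed events are those that arise and resolve in that gap without needing care. Proctitis is a weak example: in the cited phase II series it began 7 to 10 days after therapy but lasted until resection, so Pre-Op can see it. Peak grade could still be missed.

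**3. What is dropped in control.** The side effects listed under 11.8 are those of capecitabine, so the threshold reaches concurrent treatment. Before surgery only control receives chemotherapy, so the rule can only lower control's grade 1–2 totals.

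**4. Is an acute window to surgery common to both arms?** No. Endo-HDR: about 0.6 + 8 to 0.6 + 12 = 8.6 to 12.6 weeks. Control: 5.6 + 8 to 5.6 + 12 = 13.6 to 17.6 weeks.

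**5. Illustration for laboratory-only events.** The documents give no on-treatment count frequency, no per-count probability p of a recordable cytopenia, no within-patient correlation r and no test level. All are assumed here, with a two-sided 0.05 Fisher test and 46 control against 92 Endo-HDR patients. For k counts, P(ever) = 1 − (1 − p)^k when r = 0. Otherwise P(ever) = 1 − ∏(b + j)/(a + b + j), j = 0 to k − 1, with a = p(1 − r)/r and b = (1 − p)(1 − r)/r. Rejection is by exact enumeration. With both rates at 5.0% the test rejects 2.7% of the time.

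| p control / Endo-HDR | Counts control / Endo-HDR | r | Ever recorded, control / Endo-HDR | Rejects |
|---|---|---|---|---|
| 5% / 5% | 7 / 1 | 0 | 30.2% / 5.0% | 97.2% |
| 5% / 5% | 7 / 1 | 0.6 | 10.5% / 5.0% | 19.9% |
| 5% / 5% | 7 / 1 | 0.9 | 6.2% / 5.0% | 4.7% |
| 5% / 5% | 4 / 1 | 0 | 18.5% / 5.0% | 66.4% |
| 5% / 5% | 4 / 1 | 0.6 | 8.9% / 5.0% | 12.6% |
| 5% / 5% | 7 / 2 | 0 | 30.2% / 9.8% | 80.9% |
| 5% / 5% | 7 / 2 | 0.8 | 7.5% / 6.0% | 5.1% |
| 2% / 2% | 7 / 1 | 0.8 | 3.0% / 2.0% | 4.4% |
| 1% / 5% | 7 / 1 | 0 | 6.8% / 5.0% | 5.9% |
| 1% / 5% | 7 / 1 | 0.6 | 2.2% / 5.0% | 1.7% |
| 2% / 5% | 7 / 1 | 0 | 13.2% / 5.0% | 34.7% |
| 2% / 5% | 7 / 1 | 0.6 | 4.3% / 5.0% | 2.1% |

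The last four rows let the 11.8 threshold lower the recordable chance in control. The excess then shrinks or changes sign. Across plausible inputs the distortion runs from large to none.

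**The case against.** Three arguments against the point have force.

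**The blood-count difference is inferred.** The calendar lists CBC on the same schedule in both arms, and footnote 7 speaks of toxicity monitoring, not blood draws. The holds in 7.3.4 and 7.3.5 cannot be applied without some on-treatment counts, but their frequency is not stated. Nor do the documents rule out a count during Endo-HDR, since 11.5 lists anemia and pancytopenia as expected events. A reader might infer that control is sampled weekly and Endo-HDR never, so that hematologic rows are known to be biased against control. The documents do not support that. This stands, and it is why the table above is only an illustration.

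**Other text softens the gap.** Section 11.1 asks for all adverse events, including laboratory findings, to be recorded, and 11.12.1 sends all of them to case report forms. This helps with events that someone notices. It does not create a scheduled look in weeks 2 to 6, and it conflicts with 11.8 without saying which governs.

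**Monitoring during exposure is ordinary safety practice, and control should have more real toxicity.** Both are true. Neither calls for a formal between-arm test without a common window, or for a grade threshold that operates in one arm only.

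**Conclusion.** The point holds for the acute-toxicity comparison. By the plan's own rules the arms differ in scheduled checks (about 1 against 6 before Pre-Op) and in what is recorded below grade 3. The check schedule favors Endo-HDR; the 11.8 threshold favors control at grades 1 and 2. Their net size and direction in any row are unknown.

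A reader might take the high rejection rates as the false-positive rate of the planned test. They are not. The 97.2% needs seven fully independent counts per control patient against one in Endo-HDR, and it ignores 11.8. Rejection is already close to 5% at a correlation of 0.8 in some settings, and below 3% in others once 11.8 is allowed for. The figures show that unequal looks can matter, not by how much.

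The consequence is limited to one secondary endpoint, chiefly transient, mild or laboratory-only events. pCR is unaffected. The change is worth considering because it is cheap and the toxicity claim is central to the rationale for Endo-HDR.

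**What to change.** 1. **Section 11.8.** Confine the grade 3 threshold to postoperative adjuvant chemotherapy. Until surgery, record all grades in both arms whatever the attribution.
2. **Footnote 7.** Continue the weekly toxicity check in both arms through week 6 from first fraction, by phone once Endo-HDR has ended.
3. **Section 14.5.** Compare acute toxicity as worst grade over the same fixed interval from first fraction in both arms, for example through week 6. Report laboratory-only hematologic grades with the number of counts per arm. Add the shared Pre-Op count as a sensitivity comparison. It should not be the only hematologic test, because that would discard the on-treatment cytopenia that Endo-HDR is meant to avoid.

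**Cost.** Wording in three places. Calls in weeks 2 to 6: 5 × 92 = 460; at weeks 2 and 4 only, 2 × 92 = 184, with thinner coverage. Control sites record some extra low-grade events. Treatment breaks can carry control radiation past week 6, so later events should still be tabulated, outside the tested interval. No additional blood draw is required.
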